5.3 EXCLUSION CRITERIA (All groups)

- · Active bleeding when screened
- Primary neurological ICU admission diagnosis
- Patients discharged from the ICU following cardiac surgery
- Currently receiving or planned to receive end-of-life care
- Patient not expected by the clinical team to survive hospital discharge
- Patient with dialysis-dependent chronic renal failure prior to ICU admission

- Physical condition resulting in an inability to perform, a cardiopulmonary exercise test (CPET), for example, major limb trauma, amputation, or primary neurological injury (e.g. stroke, brain injury, Guillain-Barre syndrome).
- Any absolute or relative contraindication for CPET testing.
- Patient lacking mental capacity at the time of screening for eligibility
- Patients with previously adopted care escalation plan that excludes level 3 care
- Patients with a major physical disability that severely affects the activities of daily living before ICU admission

5.4 CO-ENROLMENT

Co-enrolment will occur with the ABC post-ICU trial. Other co-enrolment will be permitted only if it is in agreement with an ACCORD Co-enrolment Policy (POL008 Co-enrolment Policy).

6 PARTICIPANT SELECTION AND ENROLMENT

6.1 IDENTIFYING PARTICIPANTS

Patients discharged from the general ICU/HDU of the RIE and WGH will be screened for eligibility by doctors and nurses working in the Edinburgh Critical Care Research Group (ECCRG), who are part of the clinical critical care (direct care) team.

6.2 RECRUITMENT WINDOW

Eligible patients will be able to provide consent at any time following discharge from the ICU/HDU to hospital discharge.

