3.1 OBJECTIVES

- To provide objective figures regarding the functional capacity of critical illness survivors close to the point of hospital discharge.
 - o Cardiopulmonary exercise test (cycle-ergometer based)
- To measure patient-reported levels of fatigue during the immediate post ICU discharge period
 - Visual Analogue Scale Fatigue (VAS-F)
- To measure patient-reported performance in the daily living activities
 - Barthel Index (BI)
- To access day (daytime activity) and night movement (sleep patterns) of intensive care survivors for two months since enrollment
 - Wearable wrist-worn accelerometer (Geneactiv device)
- To explore the relationship between these variables and anaemia status following ICU discharge
- To compare several different cohorts of patients discharged from critical care in terms
 of:
 - o Fatigue levels (VAS-F)
 - Activity of daily living (BI)
 - o Physical activity and quality of sleep (accelerometery)
 - o Cardiopulmonary exercise capacity (CPET)

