4.1 Groups

We plan to recruit four different cohorts of patients:

Group one (feasibility group): 'ICU survivors'

These patients should have received level 3 care and ventilatory support for more than 24 hours in the ICU, and should not be involved in the ABC post-ICU trial. Patients who have contraindications for blood transfusion or rejected a blood transfusion if indicated might be included. Patients already involved in the other studies can be co-enrolled if the principal investigator agrees.

Group two: 'Anaemic ICU survivors - usual care (restrictive) transfusion strategy'

These patients will have consented to participate in the ABC-post ICU trial, and randomised to the restrictive strategy (transfused at a lower haemoglobin threshold).

Group three: 'Anaemic ICU survivors - liberal transfusion strategy

These patients will have consented to participate in the ABC-post ICU trial, and randomised to the liberal strategy (transfused at a higher haemoglobin threshold).

Group four: Patients who required high dependency care (Level 2 care) in the critical care unit

Participants in this group should have been treated for at least 24 hours at either ICU or HDU level, but required only level 2 care (no mechanical ventilation in the ICU or HDU; requirement for only single organ support).

4.2 Overview of proposed assessments and measurements.

Following the enrolment on the same day, all participants will be asked to complete short self-reported questionnaires about their ability to undertake activities of daily living (Barthel Index) and self-reported feelings of fatigue (VAS-F scale). Later, close to the point of hospital discharge or on the day of the cardiopulmonary test both questionnaires will be administered one more time.

In addition, on the day of enrolment, all participants will be asked to put on and wear an accelerometer device on their non-dominant wrist for up to 2 months, which is the usual time when the GENEActive accelerometer requires to be charged. Participants are encouraged to wear it for as long as possible, but taking it off is not prohibited. In the unlikely event that patients experience hypersensitivity or allergy to the device strap, they will be advised to stop wearing the strap and seek medical help by contacting medical services (either through their GP, emergency department or ambulance service).

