6.3 CONSENTING PARTICIPANTS

In order to be involved in this study, participants must have the mental capacity to give consent and personally sign and date the latest approved version of the Informed Consent form before any study-specific procedures are performed.

Potentially eligible patients will be assessed for study suitability, including their capacity to make a decision. Capacity will be determined in consultation with the direct clinical team, who are caring for the patient. For those eligible for the cardiopulmonary exercise test, the ability to undertake it will be decided by the cardiopulmonary exercise testing team, who will conduct the cardiopulmonary test later within the study. Only after a favourable decision regarding the patient's suitability is received from both clinical and cardiopulmonary exercise testing teams, the first approach to the patient will be attempted. In the post-ICU/HDU wards, a member of the research team will conduct the initial patient approach at the earliest time when the patient regains the capacity to provide informed consent after ICU/HDU discharge.

Written versions of the Participant Information and Informed Consent form will be presented to the participants detailing the exact nature of the study; what it will involve for the participant; the implications and constraints of the protocol; the known side effects, and any risks involved in taking part. It will be clearly stated that the participant is free to withdraw from the study at any time for any reason without prejudice to future care, without affecting their legal rights, and with no obligation to give the reason for withdrawal.

The recruiting window for this study is anytime following ICU/HDU discharge. The participant will be given at least 24 hours to consider the information and the opportunity to question the investigator/research team and other persons to help decide whether they will participate in the

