10.2 PROPOSED ANALYSES

A study analysis plan will be written before any analyses are undertaken.

A description of the entire cohort, length of stay, the progression of fatigue, activities of daily living over the follow-up period along with obtained objective measures of cardiopulmonary fitness, sleep pattern, daytime activity, circadian rhythms regularity and subgroups of interest (e.g ICU-AW vs No ICU-AW, had RBC transfusion vs had not) will be reported with appropriate summary measures (mean (SD), median (IQR), or n (%)).

Comparative analysis between observed groups depending on sample distribution pattern will be analysed by One-way ANOVA/Kruskal-Wallis test or unpaired T-test/Mann-Whitney test. Associations between the feeling of fatigue, daily activity, sleep pattern and functional status will be explored using correlation and regression analyses. Also, a correlation between ICU related variables, hospital readmission rate and study primary outcomes if present will be reported. These analyses will take into account the exploratory nature of the study.

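### The first fatigue and Barthel scores are tied to the consent day, not to days since ICU/HDU discharge, so unadjusted non-randomised cohort contrasts can mix cohort with stage of recovery

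*Protocol*

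**What the plan says.** - **Enrolment window.** Section 6.2: "Eligible patients will be able to provide consent at any time following discharge from the ICU/HDU to hospital discharge". Section 6.3 restates it: "The recruiting window for this study is anytime following ICU/HDU discharge". Neither gives a limit in days. Section 6.3 also directs that patients be approached as soon as they regain capacity, after clearance by the clinical and exercise-testing teams, and be given at least 24 hours to decide.
- **Timing of the scores.** Section 4.2: "Following the enrolment on the same day, all participants will be asked to complete short self-reported questionnaires". Section 7.1 and Table 2 agree. A second pair of scores is taken on the exercise-test day or near hospital discharge, but only if more than 48 hours have passed since enrolment.
- **Objectives.** Section 3.1, fatigue: "To measure patient-reported levels of fatigue during the immediate post ICU discharge period". Daily living: "To measure patient-reported performance in the daily living activities", with no period stated. A further objective begins "To compare several different cohorts of patients discharged from critical care in terms" and lists both scales. Section 3.2.2.1 places both among the primary clinical endpoints.
- **Analysis.** Section 10.2: "Comparative analysis between observed groups depending on sample distribution pattern will be analysed by One-way ANOVA/Kruskal-Wallis test or unpaired T-test/Mann-Whitney test". Regression is named for associations among outcomes, and no time term is mentioned. An analysis plan is to follow.
- **Data.** Section 8.1 lists neither the dates of unit and hospital discharge nor the time from unit discharge to enrolment.
- **By contrast,** the exercise test is anchored at 5 to 20 days after ICU discharge (sections 4.2 and 7.1).

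**The concern.** Fatigue and daily functioning are expected to change during recovery on the ward. A score fixed to the consent day may describe one patient a day or two after leaving the unit and another some weeks later. If the delay differs systematically between cohorts, a difference in mean score can appear where patients at the same stage of recovery do not differ, or a true difference can be hidden. Correlations of the scores with ICU factors are open to the same distortion, because sicker patients may regain capacity, and so be scored, later.

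The protocol's own rules give reasons to expect such differences. Group 1 was ventilated for more than 24 hours and group 4 never, so time to capacity plausibly differs. Groups 2 and 3 must first enter the parent trial, whose haemoglobin criterion can be met up to seven days after the patient is judged fit for ICU discharge. The study is exploratory, so what is at stake is interpretation, not a confirmatory error rate.

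**Working it through.** **1. The plan's own figure.** The only sample-size figure is a recruitment target. Section 10.1: 2 per month × 18 months = 36 parent-trial patients (stated 35-40); × 50% = 18 (17.5-20), against the stated 20. Adding up to 20 in the other two groups gives 38-40, against the stated 40. The target is reproduced. No alpha, power, SD or effect size is stated, so there is no power figure to check.

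**2. How late a score could fall.** Section 1 gives a hospital stay after critical care of mean 15.3, SD 22.6 days, from national audit data. For a lognormal shape (assumed), σ² = ln(1 + (22.6/15.3)²) = 1.157 and μ = ln 15.3 − 1.157/2 = 2.149. The median stay is exp(2.149) = 8.6 days; 57% of stays exceed 7 days and 32% exceed 14. A gamma shape gives 48% and 33%. These figures describe length of stay. They bound the enrolment day and do not estimate it.

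**3. Size of a timing artefact.** Assumed inputs: fatigue falls by 0.25, 0.5 or 1.0 point per week on a 0-10 scale, SD 2, and two cohorts that do not truly differ are scored 7 days apart on average. From section 5.1: 10 per group.

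- Spurious difference = slope × gap in weeks.
- Standard error = 2 × √(2/10) = 0.89.
- The last column is the rejection rate of a two-sided 5% unpaired t-test with 18 degrees of freedom (noncentral t; the 5% level is assumed).

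| Slope (points/week) | Spurious difference | In standard errors | Rejection rate |
|---|---|---|---|
| 0.25 | 0.25 | 0.28 | 6% |
| 0.5 | 0.50 | 0.56 | 8% |
| 1.0 | 1.00 | 1.12 | 19% |

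A smaller gap shrinks the effect in proportion: 4.6 days at 0.5 point per week gives 0.5 × 4.6/7 = 0.33 point.

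**4. Against what the study can see.** With 10 per group, the difference detectable with 80% power is about 1.32 SD by the t distribution, or 2.6 points at SD 2. The artefact of 0.25 to 1.0 point is roughly a tenth to two fifths of that.

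**5. Barthel.** The scoring note in appendix 16.1 treats a change of more than 2 of 20 points as probably genuine. At an assumed gain of 0.1, 0.2 or 0.3 point per day, a timing gap of 2/0.1 = 20, 2/0.2 = 10 or 2/0.3 = 6.7 days would produce 2 points.

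**The case against.** The strongest reply has five parts.

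- **Early approach is required.** Section 6.3 directs contact as soon as capacity returns. This stands as a mitigation. A reader might infer from the audit figures that about half of patients will be scored after day 7; the documents do not support that, because the figures are lengths of stay and not enrolment days. But the rule sets no limit, and time to capacity may itself follow severity.
- **Covariates belong in the analysis plan.** Largely fair. However, section 10.2 already names unadjusted tests for the cohort comparisons, and section 8.1 omits the variable that an adjusted analysis would need.
- **There is a second score.** Table 2 places it 5 to 20 days after ICU discharge, and section 10.2 does not say which score is compared between groups. This helps, but a patient enrolled within 48 hours of that assessment has only one score.
- **The dates can be recovered.** True. Consent is dated and the VAS-F form has date and time fields. The exercise-test window needs the ICU discharge date, and the three-month readmission count needs the hospital discharge date. The gap is an incomplete list, not unobtainable data.
- **The conflict is thin.** The immediate post-ICU period is undefined and could be read as the whole ward stay. For Barthel, a reader might infer a contradiction with the objective, but none exists because no period is stated; the time point is simply not fixed.

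A reader might also infer that the comparison of groups 2 and 3 is biased. Those groups are randomised, so variable timing mainly adds noise unless consent timing depends on arm. Sub-study enrolment follows randomisation, so adjusting that contrast for days to score would condition on a post-randomisation variable.

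**Conclusion.** The point holds in limited form. The first questionnaire time point is tied to consent, is not bounded in days, and does not clearly match the stated fatigue period. The non-randomised contrasts (group 1, group 4, pooled 2 and 3) and the correlations with ICU factors can therefore mix cohort with days of recovery under the stated unadjusted tests.

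The size cannot be derived from the documents. The slopes, the 7-day mean gap and the SD of 2 are all assumptions. On them the artefact is about a quarter of a standard error to just over one: enough to colour the reading of a small cohort difference, but not to dominate the results. This is an inexpensive improvement to an exploratory study rather than a flaw that undermines it.

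**What to change.** 1. In section 8.1, list days from ICU/HDU discharge to each VAS-F and Barthel score, derived from dates the study already needs.
2. Report the distribution of those days by group.
3. In section 10.2, give the non-randomised cohort contrasts and the regressions both unadjusted and adjusted for days since ICU/HDU discharge. Leave the randomised group 2 versus 3 contrast unadjusted for it.
4. Alternatively, reword the fatigue objective in section 3.1 to refer to fatigue at enrolment, before hospital discharge. This removes the mismatch in wording but not the mixing.

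The cost is one derived variable, one descriptive table and one degree of freedom in a small sample. Where delay reflects severity, adjustment may also remove part of a true cohort difference, which is why both results should be shown.

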6.3 CONSENTING PARTICIPANTS

In order to be involved in this study, participants must have the mental capacity to give consent and personally sign and date the latest approved version of the Informed Consent form before any study-specific procedures are performed.

Potentially eligible patients will be assessed for study suitability, including their capacity to make a decision. Capacity will be determined in consultation with the direct clinical team, who are caring for the patient. For those eligible for the cardiopulmonary exercise test, the ability to undertake it will be decided by the cardiopulmonary exercise testing team, who will conduct the cardiopulmonary test later within the study. Only after a favourable decision regarding the patient's suitability is received from both clinical and cardiopulmonary exercise testing teams, the first approach to the patient will be attempted. In the post-ICU/HDU wards, a member of the research team will conduct the initial patient approach at the earliest time when the patient regains the capacity to provide informed consent after ICU/HDU discharge.

Written versions of the Participant Information and Informed Consent form will be presented to the participants detailing the exact nature of the study; what it will involve for the participant; the implications and constraints of the protocol; the known side effects, and any risks involved in taking part. It will be clearly stated that the participant is free to withdraw from the study at any time for any reason without prejudice to future care, without affecting their legal rights, and with no obligation to give the reason for withdrawal.

The recruiting window for this study is anytime following ICU/HDU discharge. The participant will be given at least 24 hours to consider the information and the opportunity to question the investigator/research team and other persons to help decide whether they will participate in the

study. However, the final decision should be made within the recruitment window. Written informed consent will then be obtained. The person who obtained the consent will be suitably qualified and experienced and have been authorised to do so by the Chief/Principal Investigator. A copy of the signed Informed Consent will be given to the participant. The original signed form will be retained at the study site, and a third record added to the patient record. The decision to participate will also be recorded in the patient's electronic medical record (TrakCare; Intersystems).

Two-three months after enrolment, participants will receive a letter describing the study and explaining their involvement, including any agreement to use their data for future research. They will be given the contact detail of the Edinburgh Critical Care research team and a reminder that they can opt out of this at any time.

Although absolute and relative contraindications for undertaking the cardiopulmonary exercise test were indicated in the study's exclusion criteria, to ensure the participant's safety and suitability for the cardiopulmonary exercise test, the participant will be approached and seen by a member of the cardiopulmonary exercise team who is employed by and work within the RIE cardiopulmonary exercise laboratory.

6.3.1 Withdrawal of Study Participants

During the study, a participant may choose to withdraw from the study at any time. Participants who no longer want to be involved in the study are under no obligation to provide a reason. Their medical care will not be compromised by the decision to withdraw from the study. The patient will be asked for permission to use his/her data that has been already collected and if the patient decides to restrict usage of the data further in the research, data will be deleted. In case when the participant loses capacity during the study, the already collected data will be preserved and used in the study, considering that the participant's legal representative is not against it.

7 STUDY ASSESSMENTS

7.1 STUDY ASSESSMENTS

After obtaining participant written consent, the baseline variables along with fatigue level and disabilities in daily living will be collected during inpatient care, whereas the accelerometery data will be recorded for some time after hospital discharge (for 2 months since enrollment). Participants will have the option of omitting the CPET test if they feel it is overly burdensome to them. In addition, hospital readmission rates during the first 3 months following hospital discharge will be extracted from the electronic medical records. Relevant study data will be obtained from the sources listed below:

- Patient medical records (baseline and follow up data).
- Raw data obtained from the wearable wrist accelerometer starting from the day of enrolment until the actigraphy device is removed and posted back. The acceleration data will be analysed using analytical software provided with the GENEActive wrist accelerometer.
- Cardiopulmonary exercise test variables. After assessing for the presents of potential
 contraindications within the period of 5 to 20 days after ICU discharge or before hospital
 discharge whichever occurs first, participants will try to undergo the CPET test in full
 compliance with the latest guidelines and recommendations by Levett and colleagues
 (2018) and will be reported in the standard CPET reporting form that is accepted by the
 RIE cardiopulmonary exercise laboratory (see: appendix). The pre-test assessment,
 testing, and supervision during the test will be conducted by the RIE cardiopulmonary
 exercise testing team.

- On the day of enrollment and then, only if more than 48 hours past since enrollment, on the day of the cardiopulmonary exercise test or close to the date of hospital discharge, participants will be asked to fill in questionnaires:
 - 1. Barthel Index form (appendix)
 - 2. VAS-F scale (appendix)

7.2 LONG TERM FOLLOW UP ASSESSMENTS

Participants will be followed until the wrist-worn accelerometer's battery needs a recharge which the manufacturer states to be 45 days if the recording frequency is set to low but the collaborator of our study [name] who has used this device in his research confirmed that the battery could hold a charge for up to 2 months. On this basis, we considered recording accelerometery data for as long as possible and have set the timing of the data recording for 2 months. The device will record the participant's activity, skin temperature, and ambient light intensity automatically during the whole study period. The recorded data extraction will be made once the device is returned. In addition, the research team will make attempts to reach the participants via telephone or mail to find out whether they have any issues related to the accelerometer device appliance and remind them about their involvement in the study.

7.3 STORAGE AND ANALYSIS OF SAMPLES

No biological samples will be collected.

8 DATA COLLECTION

8.1 At baseline

The following patient data will be collected by the investigator/research team from the NHS electronic patient record (TRAK)

- Demographics: gender, sex, age.
- Functional Comorbidity Index (FCI) which is calculated based on the presence or absence of the chronic diseases (18 diagnoses) before current ICU admission;
- Acute illness characteristics: ICU admission diagnosis; APACHE II score; duration of mechanical ventilation; duration of renal replacement therapy (if required); the worst SOFA score.
- Fatigue Severity Scale and Activity of Daily Living (at the time of enrolment).
- ICU related variables: neuromuscular blocker and corticosteroid drugs use.
- Laboratory findings: haemoglobin concentration.

